3.2.1.2 Scoring of Assessment Instruments

mNIS+7

The mNIS+7 consists of two composite scores: the NIS composite score (maximum of 244 points) and the modified +7 composite score (maximum of 102.32 points).

NIS

The NIS composite score consists of 4 components:

- Cranial Nerves (NIS-C), maximum 40 points
- Muscle Weakness (NIS-W), maximum 152 points
- Reflexes (NIS-R), maximum 20 points
- Sensation (NIS-S), maximum 32 points.

Questions that make up each composite are listed in the table below.

NIS composite	Question number
Cranial Nerves	1-5
Muscle Weakness	6-24
Reflexes	25-29
Sensation	30-37

Note that each question is separately assessed for the right and left side of the body, meaning that questionnaire is comprised of 74 subcomponents (37 for the left side, and 37 for the right side).

Modified +7

The modified +7 composite score consists of 4 components:

- 1 component for autonomic nerve assessment:
 - Heart Rate to Deep Breathing (HRDB), minimum -3.72 points, maximum 3.72 points,
- 1 component for the nerve conduction assessment of the lower and upper limbs:
 - \circ Nerve Conduction Tests (Σ 5 NC), maximum 18.6 points from 5 subcomponents (PMAK, TMAK, UMAE, USAW, SSAB) with minimum -3.72 points and maximum +3.72 points each,
- 2 components for the sensory nerve assessment:
 - o Touch-Pressure (TP), maximum 40 points
 - Heat-Pain (HP), maximum 40 points.
 NOTE: Testing for both TP and HP is done at up to 10 sites on one side of the body. To obtain the full body score for TP and HP, the summation scores from all 10 anatomical sites

is multiplied by 2 (only one side of the body is tested as FAP is symmetrical neuropathy, identical results are assumed for the other side).

Component	Data entry convention /Comment	Pre-processingstep
Heart Rate Deep Breathing	If HRDB could not be measured due to pacemaker or arrhythmia, MC Core checked either the box "no reliable data to due pacemaker" or "no reliable measure points due to arrhythmia," and left the HRDB score as blank in the BioClinica database	None
	If HRDB was not measured in error or missing for other reasons, MC Core entered a "-9" into the BioClinica database	Set "-9" to missing
	Transform normaldeviate score so that larger values coincide with worse outcomes	Multiply subcomponent score by "-1"
Nerve conduction test	If the nerve attribute was not tested in error, MCCore entered a "-9" into the BioClinica database	Set "-9" to missing

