3.4.1 Descriptive Statistics

For all efficacy endpoints, descriptive summary statistics for absolute values, change or percent change from baseline, if applicable, will be provided by analysis visits for FAS and PPS.

For change or percent change from the **parent study baseline**, analysis visits are defined for Week 35 and Week 65 or 66, if applicable, from the parent study and for Week 26, Week 52, Week 78, Week 104, Week 130 and Week 156 in the OLE study. Analysis visits of Year 4 Week 52 and Year 5 Week 52 will also be included for NIS, Norfolk QOL-DN, SF-36 Questionnaire and PND Score.

For change or percent change from the **OLE study baseline**, analysis visits are defined for Week 26, Week 52, Week 78, Week 104, Week 130 and Week 156 in the OLE study. Analysis visits of Year 4 Week 52 and Year 5 Week 52 will also be included for NIS, Norfolk QOL-DN, SF-36 Questionnaire and PND Score.

By patient listings for all efficacy endpoints will be provided.

For the two primary endpoints (mNIS+7 score and Norfolk QOL-DN total score), data collected outside the analysis windows in the OLE study, e.g. before Week 26, Week 26 to Week 52, Week 52 to Week 78, Week 78 to Week 104, Week 104 to Week 130, Week 130 to Week 156, and after Week 156 will not be summarized. These data will be included in the listings.

For mNIS+7 score and Norfolk QOL-DN total score, descriptive statistics by subgroup and treatment groups of the parent study will also be provided for the following subgroups:

• Stratification factor: V30M TTR mutation (Yes, No)

- Age at the parent study screening (< 65 years old, ≥ 65 years old)
- Race (White, non-White)
- Sex (Male, Female)
- Region (North America, Europe, South America / Australasia)
- Previous treatment with Vyndagel® or Diflunisal (Yes, No) prior to the parent study
- Disease stage at the parent study screening (Stage 1, Stage 2)
- CM-ECHO Set (Included, Not included)
- Through the whole OLE study, if the patient took any Vyndaqel® (Yes, No)

3.4.2 Efficacy Endpoints: mNIS+7 Score and Components, Norfolk QOL-DN Total Score and Domain Scores

The efficacy endpoints that are statistically analyzed are the following

- Change and percent change in the mNIS+7 score from either the **parent study baseline** or the **OLE study baseline** to Week 78 and Week 156
- Change in the Norfolk QOL-DN questionnaire total score from either the parent study baseline or the OLE study baseline to Week 78 and Week 156

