3.4.3 Other Efficacy Endpoints

Descriptive statistics, as described in section 3.4.1 (but without stratification by subgroup) will also be provided for the following efficacy endpoints:

- Change and percent change in mBMI and BMI from either the parent study baseline or the OLE study baseline to Week 78 and Week 156 in the FAS and PPS
- Shift table from either the parent study baseline or the OLE study baseline in PND score from to Week 78 and Week 156 in the FAS and PPS
- Change and percent change from either the parent study baseline or the OLE study baseline in NT-proBNP in the FAS, PPS, ECHO subgroup and CM-ECHO Set. Change in log-transformed NTproBNP from either the parent study baseline or the OLE study baseline to Week 78 and Week 156 in the FAS, PPS, ECHO subgroup and in the CM-ECHO Set
- Change and percent change in the SF-36 questionnaire domain scores, including Physical Component Summary Score, Mental Component Summary Score, and Mental Health Domain Score from either the parent study baseline or the OLE study baseline to Week 78 and Week 156 in the FAS and PPS
- Change and percent change from either the parent study baseline or the OLE study baseline to Week 78 and Week 156 in NSC in the FAS and PPS
- Change and percent change from either the **parent study baseline** or the **OLE study baseline** to Week 78 and Week 156 in the NSC individual domain scores (muscle weakness, sensory [hypo/loss of sensation], sensory [paresthesia, hyper sensation], autonomic [GI/urinary incontinence], and autonomic [other than GI//urinary incontinence]) in the FAS and PPS.

Analysis for ECHO will be included in a separate SAP for the following endpoints:

- Change and percent change in GLS by ECHO from either the parent study baseline or the OLE study baseline to Week 78 and Week 156 in the parent study ECHO subgroup, OLE ECHO set and in the Cardiomyopathy-ECHO (CM-ECHO) Set
- Change and percent change in the ECHO parameters (except GLS) in the parent study ECHO subgroup, OLE ECHO set and in the CM-ECHO Set from either the parent study baseline or the OLE study baseline to Week 78 and Week 156

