8.2 Appendix 2 Scoring of Assessment Instruments

Neuropathy Symptoms and Change (NSC)

The NSC questionnaire consists of 38 questions asking about different symptoms.

A symptom is marked as present if in the judgment of the examining neurologist, it occurs more frequently or more severely than in healthy persons of the same age and gender and is due to

neuropathy. If a symptom is present its severity is graded as 1 (slight +), 2 (moderate ++) or 3 (severe +++). If the symptom is not present it is given a score of 0.

Two questions (35 and 36) are only answered by men. These are not included in the score for women.

The questions in the NSC can be divided into the following domains

Muscle weakness: Questions 1 - 19
 Sensory (hypo / loss of sensation): Questions 20 - 22
 Sensory (paresthesia, hyper sensation): Questions 23 - 29

• Autonomic (GI/Urinary incontinence): Questions 31, 32, 33, 34

• Autonomic (other than GI/Urinary incontinence): Questions 30, 35 - 38 for men

Questions 30, 37 - 38 for women

The Muscle weakness domain is also divided into 4 sub-domains:

Head and Neck: Questions 1 - 6
 Chest: Questions 7 - 9
 Upper Limbs: Questions 10 - 15
 Lower Limbs: Questions 16 - 19

For each sub-domain and domain the total score is obtained by summing the relevant questions. The maximum score is therefore 57 for muscle weakness, 9 for Sensory (hypo / loss of sensation), 21 for Sensory (paresthesia, hyper sensation), 12 for Autonomic (GI/Urinary incontinence), 15 for Autonomic (other than GI/Urinary incontinence) in men and 9 for Autonomic (other than GI/Urinary incontinence) in women. The minimum score is zero for each domain.

The NSC total score is the sum of the scores across all 5 domains. The minimum NSC total score is therefore 0 and the maximum NSC total score is 114 for men and 108 for women.

For questions 20-29 the location affected is also collected on the questionnaire but this information is not used in the calculation of the domain or total scores.

The NSC questionnaire also records a change score for the change in symptoms compared to the week before study onset. These are scored as follows

- -3 =worse ---
- -2 = worse --
- -1 = worse -
- 0 = no change
- +1 = better +
- +2 = better ++
- +3 = better +++

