9.2 Additional Analyses added for Final Analyses

9.2.1 Based on OLE data only

- Summary of disposition and protocol deviation associated with COVID-19 based on CS3
 Enrolled Patients
- Summary of ISIS 420915 Trough Plasma Concentrations (On-Study) based on safety set.
- Summary of Complement Results (Complement C3, Complement C4, Complement Split Bb, Complement Split C5a) by visit based on safety set
- Summary of TEAE by System Organ Class and Preferred Term and by PND score (On-Study)
 based on safety set
- Lab shift table for Hematology (Hemoglobin, Lymphocyte, Neutrophil, White Blood Cell), Chemistry Test, Coagulation Test, Urinalysis test, Urinalysis Results from Central Lab Based on 24-hr Urine Collections, Confirmed Peak ALT, Confirmed Peak AST, Confirmed Peak Total Bilirubin (On-study) based on safety set.
- Incidence of Post-baseline abnormality, including lab Complement Results, vital signs and body weight and QTcF.

Efficacacy endpoints

On-treatment: Add Statistical Analysis of Change from CS2 Baseline to efficacy endpoints:

mNIS+7, NIS+7, NIS, Modified +7, +7, NSC composite and component score, mNIS+7 composite score, Norfolk QOL-DN, NSC total and domain score and selected questions, SF-36 component and Domain Scores. Norfolk QOL-DN Symptoms Domain Score based on Stage 1 Patients, Norfolk QOL-DN Physical Functioning/Large Fiber Neuropathy Domain Score based on Stage 2 Patients

Post-treatment:

Show Descriptive statistics of absolute value, change from baseline and percent change from baseline in mNIS+7, NIS+7, NIS, Modified +7, +7 Composite and Component, Norfolk QOL-DN Total and Domain Scores, SF-36 Scores, NSC score and Select Questions from NSC

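### The SAP plans percent change from baseline for scores that can be zero, and in some cases negative, with no rule for those baselines

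*Combined protocol and SAP*

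**What the plan says.** Percent change appears in four places in the SAP's efficacy plan.

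- **9.2.1, post-treatment tables for the final analysis:** "Show Descriptive statistics of absolute value, change from baseline and percent change from baseline in mNIS+7, NIS+7, NIS, Modified +7, +7 Composite and Component". The same sentence adds Norfolk total and domains, SF-36, the NSC score and selected NSC questions. It carries no qualifier.
- **3.4.3:** change and percent change are listed for the NSC total and, in a separate item, to "Week 78 and Week 156 in the NSC individual domain scores".
- **3.4.1:** "For all efficacy endpoints, descriptive summary statistics for absolute values, change or percent change from baseline, if applicable, will be provided by analysis visits". Section 9.2.2.3 (integrated CS2 and CS3 efficacy) uses the same qualifier. Neither section says which scores it excludes.
- **3.4.2:** the mNIS+7 item begins "Change and percent change in the mNIS+7 score from either the". The Norfolk item begins "Change in the Norfolk QOL-DN questionnaire total score from either the", with no percent change, and the mNIS+7 components and Norfolk domains are likewise listed as change only.

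On the scales, SAP 3.2.1.2 gives "Heart Rate to Deep Breathing (HRDB), minimum -3.72 points, maximum 3.72 points". It sets the same limits for each of the five nerve-conduction subcomponents and for vibration detection threshold (VDT) in the +7. Norfolk Questions 31 and 32 score from -2 to 2. For NSC, Appendix 2 says: "The minimum score is zero for each domain".

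SAP 3.2.1.3 sets change from baseline to missing when either value is missing. It is silent on a baseline that is zero or negative.

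**The concern.** Percent change is interpretable only where zero means none of the quantity and every baseline is above zero. Two groups of scores in these tables fail that condition, in different ways.

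For scores that can be negative, dividing by a negative baseline turns a worsening into a percent improvement and an improvement into a percent worsening. For scores with a floor of zero, the quantity does not exist at a zero baseline. The patients it loses are exactly those who cannot improve, so the percent-change column describes a selected group while the absolute-change column beside it describes everyone. In both groups a baseline just above zero produces very large values that can dominate a mean.

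At stake is the readability of component, domain and single-question tables. No decision rule depends on them.

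**Working it through.** **1. Reproduce the SAP's stated maxima (3.2.1.2, 3.4.2, Appendices 1 and 2).**
- NIS: 40 + 152 + 20 + 32 = 244.
- Modified +7: 3.72 + 5 × 3.72 + 40 + 40 = 102.32.
- mNIS+7: 244 + 102.32 = 346.32.
- +7: 3.72 + 18.6 + 3.72 = 26.04.
- NSC: 57 + 9 + 21 + 12 + 15 = 114 for men; 57 + 9 + 21 + 12 + 9 = 108 for women.

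All agree with the SAP.

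**2. Sum the minima in the same way.**
- HRDB and VDT: -3.72 each. Nerve conduction: 5 × (-3.72) = -18.6.
- Modified +7: -3.72 - 18.6 + 0 + 0 = -22.32, and the same for mNIS+7 if NIS is 0.
- +7: -3.72 - 18.6 - 3.72 = -26.04, and the same for NIS+7 if NIS is 0.
- Norfolk physical functioning has 15 items, including Questions 31 and 32: minimum 2 × (-2) = -4, maximum 13 × 4 + 2 × 2 = 56. Norfolk total: -4 to 33 × 4 + 2 × 2 = 136.
- Floor of zero, never negative: NIS and its four components, touch-pressure, heat-pain, the other four Norfolk domains, and NSC total, domains and questions.

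**3. Apply the percent-change formula.** The only one written in the SAP is (post-baseline - baseline) / baseline, given in 5.2 for creatinine clearance. Using it for efficacy scores is an assumption, though it is the usual reading. Higher is worse on every score below; the baselines are illustrative.

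| Score | Baseline to visit | Change | Percent change |
|---|---|---|---|
| HRDB | -1 to 1 | +2 (worse) | 2 / (-1) = -200% |
| HRDB | -1 to -2 | -1 (better) | -1 / (-1) = +100% |
| Nerve conduction | -4 to 2 | +6 (worse) | 6 / (-4) = -150% |
| Nerve conduction | 0.5 to 4.5 | +4 (worse) | 4 / 0.5 = +800% |
| Norfolk total | -2 to 4 | +6 (worse) | 6 / (-2) = -300% |
| NSC question | 0 to 2 | +2 (worse) | undefined |
| mNIS+7 | 80 to 86 | +6 (worse) | 6 / 80 = +7.5% |

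Dividing by the absolute value of the baseline would correct the signs (for example +200% in the first row) but leaves the zero case undefined.

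**4. How often?** The documents give no baseline distribution, so only a range under assumptions is possible.
- If HRDB baselines were normal with SD 1, the share below zero would be about 16% at a mean of 1 and 0.6% at a mean of 2.5.
- If an NSC domain were Poisson at baseline, the share at exactly zero would be exp(-1) = 37% at a mean of 1 and exp(-3) = 5% at a mean of 3.

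These figures restate the assumed baselines. They show that the effect could be negligible or substantial; they do not estimate it.

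**5. Which tables will hold data?** Post-treatment for these scores means more than 52 days after the last dose (SAP 3.2.1.1.4 and 3.2.1.4). Protocol Appendix A schedules no mNIS+7, NIS or Norfolk at the 13-week post-treatment visit. Early-termination assessments are ideally within 14 days of the last dose, so they count as on-treatment. The post-treatment windows in SAP Appendix 3, Table 2 cover only NT-proBNP, BMI, mBMI and the PD panel. The 9.2.1 tables would therefore hold only stray late assessments.

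**The case against.** The case for leaving the plan alone is that little depends on these columns. The one unqualified request for percent change in components and Norfolk falls in post-treatment tables that should be nearly empty. The on-treatment line of 9.2.1 asks for change only. Elsewhere the applicability qualifier lets the programmer omit percent change, and 3.4.3 refers back to 3.4.1, so the qualifier arguably reaches NSC too. The study has no formal hypotheses, medians and quartiles accompany the means, the protocol's efficacy endpoints are changes, and NSC is not among the protocol's objectives or endpoints.

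Most of that stands, and it limits the consequence. It does not remove the defect: 3.4.3 names percent change for NSC total and domains, whose minimum is zero, 9.2.1 has no qualifier, and a qualifier that names no excluded score is not a rule.

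A reader might also infer more than the documents support:
- **That all these scores can be negative.** Only HRDB, nerve conduction, VDT, the composites that contain them, and Norfolk physical functioning and total can. The rest have only the zero problem.
- **That the main mNIS+7 tables are compromised.** A negative mNIS+7 needs the normal deviates to outweigh NIS, touch-pressure and heat-pain together. That is possible on paper but remote in patients who entered the parent study with Stage 1 or 2 polyneuropathy.
- **That 3.4.2 orders percent change for components or Norfolk.** It does so only for the mNIS+7 composite.
- **That patients with a zero baseline are lost from the analysis.** They remain in the absolute-value and change summaries.

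**Conclusion.** The point holds at this scope. The SAP plans percent change for scores on which it is not valid and gives no rule for zero or negative baselines.

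- **Sign reversal,** assuming a signed denominator: HRDB, nerve conduction, VDT, the modified +7 and +7 composites, and Norfolk physical functioning and total. Percent change is explicit for these in 9.2.1 and left open in 3.4.1 and 9.2.2.3.
- **Undefined at zero:** NSC total and domains (explicit in 3.4.3), and NSC selected questions, NIS components, touch-pressure, heat-pain and the other four Norfolk domains (explicit in 9.2.1).

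The frequency cannot be derived from the documents. The consequence is misleading or missing entries in descriptive tables, of which the on-treatment NSC tables are the clearest populated case. SF-36 is left aside because the SAP states no score range for it.

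**What to change.** - **9.2.1:** delete percent change for the modified +7 and +7 composites, the components of mNIS+7, NIS+7 and NIS, Norfolk total and domains, and the NSC score and selected questions.
- **3.4.3:** delete percent change for NSC total and domains.
- **3.4.1 and 9.2.2.3:** state that percent change is not applicable to these scores, so that the qualifier has a defined meaning.
- **Report** the absolute change, which is already planned for all of them.
- **Keep** percent change, if wanted, for the mNIS+7, NIS+7 and NIS composites, provided patients with a baseline of zero or below are excluded from that column and their number is shown. It can stay without conditions for BMI, mBMI, TTR, RBP4 and NT-proBNP, which are strictly positive.

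The cost is SAP wording and the loss of a few descriptive columns. No data collection or patient procedure changes.

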9.2.2 Based on both CS2 and CS3 data

CS3 final CRS will include some outputs from 420915 ISS, Please reference 420915 ISS SAP for planned statistical analyses and definition in details. Below are updates were added based on CS3 final CRS additional request

9.2.2.1 Add More Population Definition

- ISIS 420915 Full Analysis Set (ISIS 420915 FAS) will be subset of CS2 or CS3 FAS patients who
 received at least 1 injection of ISIS 420915 in CS2 or CS3 studies.
- ISIS 420915 ECHO subgroup will be the subset of CS2 ECHO subgroup patients who received at least 1 injection of ISIS 420915 in CS2 or CS3 studies.
- ISIS 420915 CM-ECHO Set will be the subset of CS2 CM-ECHO Set patients who received at least 1 injection of ISIS 420915 in CS2 or CS3 studies.
- ISIS 420915 PK Set will include all patients who received at least one dose of ISIS 420915 and have at least one evaluable PK sample collected and analyzed with reportable result in CS2 or CS3 studies.

9.2.2.2 Study Period Definition (On-Treatment, Post-Treatment and On-Study)

On-Treatment

- For efficacy endpoints except BMI, mBMI and PD, on-treatment period starts from ISIS
 420915 Study Day 1 until 52 days after the last dose of ISIS 420915.
- For BMI, mBMI, PD and Safety endpoint ERG, on-treatment period is from ISIS 420915 Study
 Day 1 until 28 days after the last dose of ISIS 420915
- For other Safety endpoints except ERG, on-treatment period is from ISIS 420915 Study Day
 until 7 days after the last dose of ISIS 420915

Post-Treatment

Post-treatment period starts on the day after the on-treatment period and ends on the day
of the patient's last contact date within the study.

On-Study

On-Study starts from ISIS 420915 Study Day 1 until the patient's last contact date.

Of note, the definition above only apply for CS2 and CS3 combined data summary, which is not conflict with section 3.2.1.1.4

9.2.2.3 Itegrated Summary of Efficacy based on CS2 and CS3 data

Descriptive summary statistics:

Descriptive summary statistics for absolute values, change or percent change from ISIS 420915 baseline, if applicable, will be provided by analysis visits for below endpoints based on 420915 FAS, unless specify.

- mNIS+7 Composite Score (On-Treatment)
- mNIS+7 Composite Score (On-Treatment) by IM
- Modified +7 and +7 Composite Scores (On-Treatment)
- NIS+7 Composite Scores (On-Treatment)
- NIS Composite and Component Scores (On-Treatment)
- Modified +7 Component Scores (On-Treatment)
- +7 Component Scores (On-Treatment)
- Norfolk QOL-DN Total Score (On-Treatment)
- Norfolk QOL-DN Total Score (On-Treatment) by IM
- Norfolk QOL-DN Symptoms Domain Score (On-Treatment) Stage 1 Patients
- Norfolk QOL-DN Physical Functioning/Large Fiber Neuropathy Domain Score (On-Treatment)
 Stage 2 Patients
- Norfolk QOL-DN Domain Scores (On-Treatment)
- NSC Total Score and Domain Scores (On-Treatment)
- Modified Body Mass Index and Body Mass Index (On-Treatment)
- Transthyretin (TTR) and Retinol Binding Protein 4 (RBP4) (On-Treatment)
- Transthyretin (TTR) (On-Treatment) by IM
- SF-36 Component Summary Scores and Domain Scores (On-Treatment)
- NT-proBNP Result (pmol/L) and Log-Transformed NT-proBNP Result (On-Treatment), outputs will be repeated based on ISIS 420915 CM-ECHO set
- mNIS+7, NIS+7, NIS, Modified +7, +7 Composite and Component Scores (Post-Treatment)
- Norfolk QOL-DN Total and Domain Scores (Post-Treatment)
- SF-36 Scores (Post-Treatment)
- NSC Score (Post-Treatment)
- Global Longitudinal Strain (%) (On-Treatment) based on ISIS 420915 Enrolled Patients, ISIS 420915 ECHO Subgroup, and ISIS 420915 CM-ECHO Set
- Assessment of Global Left Ventricular Size and Function LV Mass (g) (On-Treatment) based on ISIS 420915 Enrolled Patients, ISIS 420915 ECHO Subgroup, and ISIS 420915 CM-ECHO Set
- mNIS+7 Composite Score: Response Rate by Threshold Value by Visit (On-Treatment) based on ISIS 420915 FAS

- Summary of PND Score Shift from Baseline by Visit (On-Treatment) based on ISIS 420915
 FAS
- Summary of PND Score Change from Baseline by Visit (On-Treatment) based on ISIS 420915
 FAS
- Summary of Select Questions from NSC (On-Treatment) and (Post-Treament) based on ISIS 420915 FAS

